
11.0 Data Analysis and Data Management

Data Analytic Plan for Aim 1 Qualitative Data

Qualitative data from interviews, quantitative data from questionnaires, and video and audio recordings will be incorporated for mixed methods data analysis⁶⁶. This approach was chosen because, while quantitative data can identify usability errors and areas of dissatisfaction, qualitative data provides guidance on the root of errors and methods for optimization. Qualitative data will be analyzed using NVivo software⁶⁷ and a deductive/inductive template analysis approach^{68,69} using iterative codes to identify core concepts⁷⁰. From these core concepts, we will determine the needs, concerns, and impressions of our prototypes. Two coders will independently review and code data using an iterative, team-based process with discrepancies resolved by the study team. Qualitative themes will be supplemented by patterns identified in quantitative results. After completing qualitative and quantitative data analysis independently, data from each source will be synthesized using graphical matrix configurations for data triangulation⁷¹. This analytic approach was selected due to the expectation that participants will raise unanticipated needs. Mean ratings of VapeX components from the After-Scenario Questionnaires (ASQs) will be calculated and components with lowest satisfaction will be flagged for refinement. Video and audio recordings be coded for navigation errors (difficulty locating a function), content errors (difficulty due to information labeling), and usage errors (improper tool use). Problems will be grouped according to severity (critical/serious/minor).

Sample Size Estimation

As a pilot, our goal is to determine VapeX feasibility/acceptability and estimate effect sizes for a larger Phase II project. We can obtain more robust estimates in the VapeX group via 1:1 randomization with the first 5 being assigned to the VapeX group for usability testing. Toward these ends, we will randomize **49 to VapeX and 49 to TAU**. To account for 20% attrition, we will enroll a maximum of 108 participants.

Data Analytic Plan for Aim 2

Feasibility and Acceptability. Within the VapeX group, retention will be defined as the proportion of participants who use the app at least once within each week following enrollment. Retention point estimates and 95% CIs will be calculated, and a one-sided, one-sample proportion test will be used to determine whether retention is at least 70% (or higher) within each group. Other metrics of feasibility/acceptability (ease of use, continued desire to use, etc.) will be summarized within group via summary statistics and 95% CIs, as appropriate.

Vaping Behavior and Vaping Cessation Outcomes. Descriptive statistics will be calculated and compared for overall group differences via Fisher's exact tests, chi-square tests, or nonparametric equivalents, as necessary, for baseline variables. Pairwise differences will be explored for categorical variables that show a significant overall group difference to see where differences may exist. Significant baseline demographic differences between groups will be included as covariates in vaping and depression outcomes analyses. Descriptive statistics (e.g., means, frequencies, percentages) will be calculated for the primary vaping-related outcomes including frequency of vaping and other tobacco product use (number of e-cigarette use episodes per day, number of days using an e-cigarette per week, number of days using other tobacco products including cigarettes) and vaping cessation outcomes (number and duration of e-cigarette quit attempts, 7-day point prevalence abstinence at Week 4) overall and by treatment group. To examine group differences adjusted for relevant covariates based on baseline differences between groups, generalized linear mixed models with logit links for binary outcomes will be used, including a random component for participant and/or clinic. These mixed models will account for any clustering effects within participant and clinics.

Depression. Similar generalized linear mixed models will be used to examine group differences (VapeX vs. TAU) in depression (BDI-II) over time along with an interaction between group and time adjusting for baseline differences and baseline depression. All models will include a random component to account for any clustering effects from the clinic from which the participant was recruited along with a random effect for repeated measures within an individual. Sex will be examined for inclusion as a covariate in all models. These generalized linear models allow for examination of overall main effects of group, time, and the interaction between group and time, while also accounting for repeated measures within participants and clustering with clinics^{72,73}.

Missing Data. All randomized participants will be included in primary analyses, and imputation methods will be used to accommodate missing data if missing data is >10%. Sensitivity analyses will be done using only those with complete data, with results compared to primary analyses. Attrition will be assessed to determine whether there is differential dropout by group.

Adverse Events (AEs). AEs will be defined as a clinically significant (i.e., 10-point⁶⁴) increase in depression on the BDI-II from baseline or any incidence of suicidality (response of "I would like to kill myself" or "I would kill myself if I had the chance" on the BDI-II suicidality item). We will determine the incidence of AEs and associated 95% CIs. A chi-square test will determine if the rate of AEs is greater than 5% in any group.

Data Management

Regarding questionnaire data, data will be obtained for research purposes only. The recruitment project is stored in REDCap and only study team members will have access to the recruitment project database. The research team will only have access to the REDCap recruitment project while actively enrolling for the study. The recruitment project will be stored separately from the project containing research data. The recruitment REDCap project will potentially contain both identifiers and health information in the same project. All data will be collected, stored, and managed via REDCap, which is a secure, web-based application designed exclusively to support data capture for research studies. REDCap provides secure, web-based flexible applications, including real time validation rules with automated data type and range checks at the time of entry. The underlying database is hosted in a secure data center at MUSC, a secure environment for data systems and servers on campus, and includes redundancy, failover capability, backups and extensive security checks. The system has several layers of protection including user/group account management, "Data Access Groups" which allow data to be entered by multiple groups in one database with segmented user rights for entered data, audit trails for all changes, queries and reports, and Secure Sockets Layer (SSL) encryption. Name and relevant contact information will be obtained to provide compensation and every effort will be made to maintain subject confidentiality, in accordance with HIPAA. All data will be identified only by code numbers (participant IDs). Participant IDs will be linked to participants' names in a password-protected file that is accessible only to the PI and trained research staff.

12.0 Provisions to Monitor the Data to Ensure the Safety of Subjects (if applicable)

This section is based on the recommendations in NIDA's "Guidelines for developing a Data and Safety Monitoring Plan" as well as NCI's "Essential Elements of a Data and Safety Monitoring Plan for Clinical Trials Funded by the National Cancer Institute".

Summary of the Protocol

This R41 application consists of a 2-Aim proposal. In Aim 1, targeted end-users, defined as adolescent (ages 16-20) regular nicotine vapers (vaped on ≥ 20 days out of the last 30⁴⁶) with elevated depressive symptoms (score of ≥ 10 on the PHQ-9⁴⁷) who have been seen at least once in the last year by a PCP, will be recruited for individual interviews (n=10) that will inform the development of VapeX. In Aim 2, we will conduct a two-arm pilot feasibility randomized controlled trial (N=106; 1:1 randomization) with the first 5 participants recruited for usability testing and randomized to receive the VapeX app, to examine the feasibility and acceptability of VapeX as well as treatment efficacy for depression and nicotine vaping cessation relative to TAU.

Trial Management

The study will be managed from the Addiction Sciences Division within the Department of Psychiatry and Behavioral Sciences at the Medical University of South Carolina (MUSC). Recruitment, data collection, data management, and treatment provision will be coordinated and centrally managed at our research lab at MUSC and will be implemented within local Family Medicine/Primary Care clinics that are part of MUSC's Primary Care ICCE.

Data Management and Analysis

Participants will enter data in REDCap, a secure, web-based application designed exclusively to support data capture for research studies. REDCap provides: 1) an intuitive interface for data entry (with data validation); 2) audit trails for tracking data manipulation and export procedures; 3) automated export procedures for seamless data downloads to common statistical packages (SPSS, SAS, Stata, R); 4) procedures for importing data from external sources; and 5) advanced features, such as branching logic and calculated fields. These procedures are effective in minimizing data entry errors (e.g., missing or errant

data). All data from VapeX will be stored on a HIPAA-compliant server. Data analytic plans are outlined above.

Quality Assurance

Accuracy and completeness of the data collected will be ensured by weekly review. The REDCap system does not accept outliers, illogical response patterns, etc. The PI and research assistant will have weekly meetings to discuss any qualitative comments received during data collection and any problems in data collection. The PI will examine the database for potential irregularities monthly. Initial data analyses will examine distributions of variable scores and comparability of baseline characteristics across conditions (for Aim 2) in case analyses need to be adjusted for these. Confidentiality procedures are outlined above.

Regulatory Issues

This study will be registered on ClinicalTrials.gov. The study does not require an Investigational Device Exemption (IDE) from the FDA. All serious AEs will be reported to the MUSC Committee on Human Research within 48-hours. Follow-up of all unexpected and serious AEs will also be reported. All AEs will be reviewed weekly by the PI and yearly by the IRB. Any significant actions taken by the local IRB and protocol changes will be relayed to the funding agency. We estimate the significant AE rate to be very low (<5%). If monthly monitoring indicates the rate is above this, we will convene a meeting of the DSMB. Potential conflicts of interest (COI) will be reported using the rules of MUSC's COI committee.

Trial Safety

The potential risks and benefits and methods to minimize these risks are outlined in the "Risks to Subjects" section. We will determine if any AEs result in dropouts or are serious according to FDA guidelines. The PI ([name]) will serve as the Program Manager for AEs. All unexpected AEs will be monitored while they are active to determine if treatment is needed. We anticipate that AEs will be rare given that the VapeX app is non-invasive and that all participants will be engaged with current healthcare. Nonetheless, any AEs will be coded on a weekly basis using the FDA's COSTART rules⁷⁴ and entered into a database. For each weekly study meeting, the research assistant will prepare a summary of all AEs, including their severity, whether they caused a dropout, required treatment, and presumed relation to app utilization. The PI will review this at the weekly study meeting (or before if more urgent). At the weekly meeting (or before if urgent), the research assistant will report any premonitory symptoms to suggest emergence of a serious psychiatric condition (e.g., suicidality). [name], a board-certified Family Medicine physician, will be available on an ad-hoc basis for on-site medical supervision for any issues that cannot be resolved by [name].

Study procedures will follow the FDA's Good Clinical Practice Guidelines and our research team has found Spilker's comprehensive text on conducting clinical trials to be useful⁷⁵. We will encourage participants to notify their physicians that a) they are in a randomized controlled research study examining a treatment for depressed mood and nicotine vaping, and b) the physician should contact the PI directly if the physician has any questions.

The research assistants will be instructed not to reveal whether a person is a participant in the study and will report to the PI any outside requests for information about a participant or any breaches in confidentiality. All requests by participant's physicians and other medical providers will be referred directly to the PI.

Trial Efficacy

The Data and Safety Monitoring Board (see below) may request a blinded interim efficacy report (blinded to the PI and research team) for review while the trial is ongoing. Final (fully unblinded) efficacy analysis will occur after all participants have completed all follow-ups.

Data and Safety Monitoring Plan Administration

The PI will be responsible for monitoring the trial, with additional oversight provided by study co-Investigators. The PI will examine monthly the outcomes database for missing data, unexpected distributions or responses, and outliers. The PI will check weekly the AE database prepared by the research assistant immediately prior to the lab meeting. A DSM report will be filed with the IRB and funding agency on a yearly basis, unless greater than expected problems occur. The report will include participant characteristics, retention and disposition of study participants, quality assurance issues and reports of AEs, significant/unexpected AEs and serious AEs. We will report efficacy at the end of the trial.

Data and Safety Monitoring Board Plan

We will create a Data and Safety Monitoring Board (DSMB), comprised of 3 clinicians with expertise in adolescent depression and substance use treatment, primary care, and clinical trials, as well as a statistician. The DSMB will meet once prior to beginning Aim 2 enrollment, once during Aim 2 enrollment, and once following study completion to review any AEs related to the study, as well as review any data management related errors. The board may be called at any point if needed for unexpected, serious AEs, etc. Modification will be made in the procedures and/or the protocol if necessary based on the findings of the board.

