1.0 Objectives / Specific Aims

The goal of this Stage 1 treatment study is to develop, systematically refine, and clinically evaluate a depression-specific Brief Behavioral Activation (BA) for adolescent vaping cessation mobile app (“VapeX”).

Aim 1: Develop and refine VapeX. Individual interviews with end-users (n=10) will inform the design of VapeX.

Aim 2: Via a two-arm pilot randomized controlled trial (N=106, randomized 1:1), examine the feasibility and efficacy of 1) VapeX vs. 2) treatment as usual. Subsequent iterative usability testing (n=5, or until saturation) will guide app refinements. Main outcomes, which will be assessed across 4-weeks of follow-up, include: 1) treatment feasibility, 2) treatment acceptability, 3) change in depression over time as a function of treatment, and 4) changes in vaping behavior (e-cigarette use episodes per day, days using an e-cigarette per week, number/duration of quit attempts, 7-day point prevalence abstinence at Week 4, use of other tobacco products) as a function of treatment.

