6.0 Number of Subjects

We will recruit up to 10 participants for individual interviews and 106 for the RCT, the first 5 of the RCT will be for usability testing.

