quitting, 2) Interactive questions to identify past quit attempts and contributors to relapse, 3) Setting a quit date, suggested to be no later than two weeks after treatment initiation, and 4) Identification of triggers and development of coping strategies. As in prior projects, to develop VapeX, we will follow an agile software development approach⁵⁴. Key phases of development will include whiteboard design, wireframing of user stories, graphic design, programming, and deployment. Development will be led by MountainPass Technology LLC, with iterative testing completed by the PI and co-Is.

HIPAA Compliance

Regarding user privacy while using VapeX, users will create a username and password in order to login to their account without storing their true identity. In VapeX, we will store a one-way hashed version of the patient's email address to support password reset and unique identification, but that identification will not be traceable back to the user's true identity. We will not store any personally identifiable information (e.g., first name, last name, email address, phone number) of users in our app database. VapeX will be HIPAA compliant. We will use a HIPAA-compliant server protected by industry-standard safeguards to prevent unauthorized access. Since we are not associating patient health information with personally identifiable information there will not be a risk of unauthorized release of patient medical data in the event of a security breach. User personal information will be contained behind secured networks and will only be accessible by the investigators, who will have special access rights to such systems. In addition, all sensitive information users supply will be encrypted via Secure Socket Layer (SSL) technology. We will not sell, trade, or otherwise transfer personally identifiable information to outside parties. Our privacy policy will be available within the app for users to view at any time. This plan is consistent with that used by our partnering app development company, MountainPass Technology LLC, in several other previous products with similar protection requirements. [name] from MountainPass Technology has expertise in HIPAA-compliant software development and will oversee all aspects of HIPAA compliance within this project.

Aim 2: Pilot Feasibility RCT (N=106) of VapeX vs. TAU.

Procedures

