After completing determination of eligibility and consent, usability testing will commence. Recruitment will continue until we reach data saturation (planned n=5)⁵⁶. The first 5 participants enrolled will be assigned to the VapeX group to assess to capture any app refinements necessary at the start of the trial. All other procedures while remain the same across participants. The remaining participants (n=98) will be randomized via REDCap 1:1 to VapeX or TAU. Participants will be randomized via a mixed block design stratified by age, baseline depressive symptoms, and concurrent depression treatment. All participants will complete baseline assessments remotely and if randomized to VapeX, study staff will remotely provide participants with app download codes and will ensure successful downloads. Study staff will then give participants brief overviews regarding app utilization and will provide the participants 10 minutes to use the app and ask questions.

Assessments

Participants will be text messaged or emailed a REDCap link to complete follow-up assessments **weekly for 4 weeks**. Assessments are estimated at 20 minutes each. Participants will be compensated in electronic gift card codes (e.g., Amazon) emailed to participants in the amount of \$20 for completion of each assessment with a \$50 bonus if all are completed. If a participant does not meet final eligibility at baseline, they will be compensated \$20 for the visit but will not be enrolled. Enrolled participants may also refer others to this study. If they refer someone that is eligible and enrolls they will receive an additional \$40 (Total possible compensation = \$190). If fraud is detected within the surveys, the Principal Investigator may decide to withdraw a participant from the study. Fraud may include 1) a research assessment being completed in an unusually short period of time, 2) straightlining (i.e., responding with the same answer to

all items on a survey), 3) inaccurate responses to a validity check question. If fraud is suspected, the study team may request additional verification of identity such as a photo ID prior to trial enrollment.

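### The enrolment figures do not add up (5 + 98 = 103, not 106), and a maximum of 108 is not a 20% attrition allowance on any stated total

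*Combined protocol and SAP*

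**What the plan says.** Three totals appear for the randomised part of the study.

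- **103 (by addition).** Section 10.0, Procedures: "The first 5 participants enrolled will be assigned to the VapeX group", and then "The remaining participants (n=98) will be randomized via REDCap 1:1 to VapeX or TAU". Section 11.0, Sample Size Estimation, agrees: it randomises "49 to VapeX and 49 to TAU", "with the first 5 being assigned to the VapeX group for usability testing".
- **106.** Section 6.0 plans "106 for the RCT, the first 5 of the RCT will be for usability testing", so the five are inside the 106. The Aim 2 heading in section 10.0 reads "Pilot Feasibility RCT (N=106) of VapeX vs. TAU". Sections 1.0 and 12.0 (Summary of the Protocol) also give 106 with 1:1 randomisation.
- **108.** Section 11.0, straight after the 49 and 49: "To account for 20% attrition, we will enroll a maximum of 108 participants". It does not say which base the 20% applies to, or whether 108 includes the five usability participants.

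Two provisions could add people. Sections 1.0 and 10.0 let usability testing run to saturation, with five planned. Section 13.0 (clinical deterioration) provides for an extra recruit when a participant deteriorates.

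**The concern.** Enrolled and randomised totals are fixed headcounts and should add exactly. Here they do not, and no section says how 103, 106 and 108 relate. The attrition sentence tells the reader that a 20% loss has been provided for, but the only figure offered in support is too small for that on any stated base.

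At stake are the enrolment limit, the number randomised per arm, and what a reader expects to remain at Week 4 in a pilot whose purpose is to judge feasibility and estimate effect sizes for a larger trial.

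**Working it through.** **Inputs.** Usability participants: 5 (sections 6.0, 10.0, 11.0, 12.0). Randomised: 98, as 49 + 49 (sections 10.0, 11.0). Stated total: 106 (sections 1.0, 6.0, 10.0, 12.0). Attrition 20% and maximum 108 (section 11.0).

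**Step 1: headcount.**
- 5 + 49 + 49 = 103, against 106: a gap of 3.
- Taking section 6.0 literally, 106 − 5 = 101 would be randomised, not 98.
- Taking 98 as randomised, 106 − 98 = 8 usability participants would be needed, not 5.

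**Step 2: try to reproduce 108.** Two forms of allowance are in common use: n / (1 − d), which leaves n after a loss of d, and the simpler n × (1 + d). With d = 0.20, rounded up:

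| Base n | n × 1.2 | n / 0.8 |
|---|---|---|
| 98 | 117.6 → 118 | 122.5 → 123 |
| 103 | 123.6 → 124 | 128.75 → 129 |
| 106 | 127.2 → 128 | 132.5 → 133 |

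None gives 108. A 10% mark-up on 98 does (98 × 1.10 = 107.8), but the plan does not say that this is where 108 came from.

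**Step 3: what 108 covers if 98 are to remain.**
- If 108 includes the five: 108 − 5 = 103 randomised, and 1 − 98/103 = 4.9%.
- If all 108 were randomised: 1 − 98/108 = 9.3%.

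**Step 4: what a 20% loss leaves.**
- 108 enrolled: 0.8 × 108 = 86.4, about 86.
- 103 randomised (108 less the five): 0.8 × 103 = 82.4, about 82.
- 98 randomised: 0.8 × 98 = 78.4, about 78; per arm 0.8 × 49 = 39.2, about 39.

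On none of these readings do 98 remain after a 20% loss.

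**The case against.** The strongest reply is that the headcount was never meant to be rigid. Usability testing may run past five, section 13.0 allows extra recruits, and 108 is called a maximum, not a target. These provisions could lift the count above 103. But no section uses either to derive 106 or 108, and sections 6.0, 10.0, 11.0 and 12.0 all speak of the first five. A ceiling said to absorb 20% attrition should still do so. What stands is that a repair which fixes the totals but ignores these two provisions would leave the plan open-ended.

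The second reply is that the consequence is small, and this is right. The study is a pilot, and section 11.0 gives no power, precision target or required number of completers. A reader might infer that the trial is underpowered, or that 123 must be randomised so that 98 remain. The documents support neither: nothing says that 98 is a number of completers to be protected.

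A reader might also infer that five non-randomly allocated VapeX participants will enter the between-group comparison, because section 12.0 describes them as *randomized* to the app and the Missing Data paragraph of section 11.0 bases the primary analyses on everyone randomised. That rests on one word in a summary. The operative text in sections 10.0 and 11.0 says *assigned*, and section 10.0 randomises only those who come after the five. The natural reading already leaves them out, so aligning section 12.0 is a minor correction.

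**Conclusion.** The figures are wrong as written and should be corrected. The headcounts differ by 3 (103 against 106). The maximum of 108 falls short of a 20% allowance on 98 by 10 (118) or 15 (123), and by more on 103 or 106. If 98 are to remain, it covers a 4.9% loss when the five are counted inside 108, and at most 9.3% when all 108 are randomised. The plan does not say which of these applies, so both are shown. The step 2 result concerns a 20% allowance applied to the stated totals, since section 11.0 names no narrower base. No power claim is affected. The documents do not show which total is intended, so that choice belongs to the sponsor.

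**What to change.** State one set of figures (usability participants, number randomised per arm, total enrolled) in sections 1.0, 6.0, 10.0 (Aim 2 heading and Procedures), 11.0 and 12.0, and replace the 20% sentence in section 11.0 with a true one. Either:

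- **(a)** keep 49 + 49 = 98 randomised and 103 enrolled, and state that 20% attrition would leave about 78 at Week 4 (39 per arm); or
- **(b)** keep 108 as the total enrolled, including the five; change the number randomised in sections 10.0 and 11.0 to 103 (52:51 is acceptable under 1:1 allocation); and state that this covers a 4.9% loss if 98 are to remain, or that a 20% loss leaves about 82.

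Under either option, say whether usability participants beyond five (sections 1.0, 10.0) and additional recruits under section 13.0 count toward the maximum.

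As a minor alignment, describe the first five in section 12.0 as assigned rather than randomised, and confirm in the Missing Data paragraph of section 11.0 that they are outside the randomised between-group comparison.

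The cost is wording, and neither option exceeds the current maximum of 108. The downside is that the stated attrition cover becomes less favourable than the present text suggests.

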4.0 Study Endpoints (if applicable)

Primary outcome variables include:

Depression. The PHQ-8 will be used for preliminary screening and the PHQ-9 will be administered at final screening. Across all timepoints depressive symptoms will also be assessed via the Beck Depression Inventory-II (BDI-II). The BDI-II is a validated assessment of depressive symptoms among adolescents and is our primary depression outcome. Self-report and Electronic Health Record (EHR) data will be used to categorize concurrent depression treatment (therapy, medications) at baseline and across the trial.

Vaping. Nicotine vaping and quit outcomes will be assessed at each follow-up using a Timeline Followback for the last 6-months at baseline and since prior follow-up for each subsequent assessment. Frequency of vaping will be assessed in multiple ways including number of vaping episodes per day and number of days per week vaping. Use of other tobacco products and frequency of use will also be assessed. Cessation outcomes include: 1) number of quit attempts since last assessment, 2) duration of each quit attempt, 3) point-prevalence abstinence, and 4) continuous abstinence. E-cigarette dependence

will be assessed at baseline via the 10-item Penn State Electronic Cigarette Dependence Index (ECDI). Participants will report motivation to quit and confidence in quitting using a modified Contemplation Ladder.

Treatment Utilization. VapeX utilization will be tracked via analytics data. Specifically, we will examine 1) number of app sessions, 2) average time per session, and 3) total time using the app. Additionally, we will assess engagement with each individual component of the app. Analytics will be examined within each week and across the entire trial duration.

VapeX Feasibility and Acceptability. VapeX participants will self-report feasibility and acceptability at all follow-ups. As in our prior trials, participants will report: 1) ease of app use, 2) continued desire to use the app, 3) perceived benefits of using the app, and 4) suggested improvements.

Assessment Grid

	Screening	Baseline	Week 1	Week 2	Week 3	Week 4
Screening Questionnaire	x					
PHQ-8	x					
Demographics		x				
PHQ-9		x				
BDI-II		x	x	x	x	x
Current use of Psych Meds		x	x	x	x	x
TLFB		x	x	x	x	x
Cessation outcomes		x	x	x	x	x
ECDI		x	x	x	x	x
Contemplation Ladder		x	x	x	x	x
Tech Comfort		x				
Feasibility/Acceptability			x	x	x	x
VapeX Usability Scale			x	x	x	x
VapeX Utilization			x	x	x	x

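### The analysed adverse event rate rests only on BDI-II answers, although section 12.0 requires a wider set of events to be coded and reported

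*Combined protocol and SAP*

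**What the plan says.** Section 11.0, under Adverse Events, gives a closed definition with two limbs: a 10-point "increase in depression on the BDI-II from baseline or any incidence of suicidality". Suicidality is then limited to two named responses "on the BDI-II suicidality item). We will determine the incidence of AEs and associated 95% CIs". The same paragraph adds: "A chi-square test will determine if the rate of AEs is greater than 5% in any group". Section 13.0 uses the same two triggers for what it calls clinical deterioration.

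Section 12.0 speaks of AEs more broadly. Under Regulatory Issues: "All serious AEs will be reported to the MUSC Committee on Human Research within 48-hours", with follow-up of unexpected events as well. Under Trial Safety: "We will determine if any AEs result in dropouts or are serious according to FDA guidelines". Events are to be coded weekly with COSTART and summarised by severity, dropout, treatment required and presumed relation to the app. The yearly monitoring report is to list AEs, significant or unexpected AEs, and serious AEs as distinct classes.

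The assessment grid in section 4.0 has a weekly BDI-II but no row asking about AEs. The nearest row is "Current use of Psych Meds". Section 13.0 describes the BDI-II as a weekly online self-report survey and lets participants decline any question.

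**The concern.** The rule that produces the reported AE incidence does not match the events that the safety section treats as AEs. COSTART coding, an unexpected class and an FDA seriousness judgement have little purpose if every AE is one of two questionnaire results.

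Suppose an event becomes known in a clinician's risk call or from a participant's physician, and no BDI-II answer meets the rule. It can be reported under section 12.0, yet it is absent from the section 11.0 incidence. A transient episode in a week when the survey is skipped is lost in the same way, as is anything that happens after a participant stops responding. If response differs between arms, so does the chance that an event is counted. The participants are 16 to 20 years old and were selected for elevated depressive symptoms, so a published AE rate will be read as a statement about safety.

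**Working it through.** The plan states no expected AE count, power or sample size for this analysis, so there is no figure to reproduce. The check has two parts.

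**1. The texts side by side**

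| Feature | Section 11.0 (analysis) | Section 12.0 (safety reporting) |
|---|---|---|
| What counts | 10-point BDI-II rise, or one of two BDI-II answers | AEs, including serious by FDA guidelines, unexpected, needing treatment, causing dropout |
| Source | BDI-II survey only | Not restricted |
| Scheduled collection | Weekly BDI-II | None stated; no AE row in the section 4.0 grid |
| Use | Incidence, 95% CI, 5% test | IRB, funder and DSMB reporting |

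No other section supplies a general AE definition that would join the two columns.

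**2. What incomplete capture does to the 5% test (illustration)**

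Inputs: group size from section 11.0, "49 to VapeX and 49 to TAU"; threshold 5%. The significance level and sidedness are not stated, so two-sided 0.05 is assumed. The share of events that the BDI-II rule captures is not in the documents and is varied from 100% to 50%.

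- Expected events at 5%: 49 × 0.05 = 2.45. One uncounted event moves the rate by 1/49 = 2.04 percentage points.
- One-sample chi-square on 1 df: (x − 2.45)² / (49 × 0.05 × 0.95), with denominator 2.3275 and critical value 3.841.
- x = 5: 2.55² / 2.3275 = 2.79, not significant.
- x = 6: 3.55² / 2.3275 = 5.41, significant. So 6 of 49 (12.2%) are needed. The exact one-sided probability of 6 or more at a true 5% is 0.035.
- Chance of at least 6 counted events: the binomial upper tail with n = 49 and p = true rate × share captured.

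| True rate | 100% captured | 90% | 80% | 50% |
|---|---|---|---|---|
| 10% | 0.365 | 0.277 | 0.195 | 0.035 |
| 15% | 0.764 | 0.664 | 0.544 | 0.159 |

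The 100% column shows what the small sample already costs. Only the fall across a row is due to the definition and collection.

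**The case against.** The strongest reply is that safety reporting does not depend on section 11.0. Section 12.0 sends serious AEs to the IRB within 48 hours, follows up unexpected ones, keeps a weekly coded AE database, monitors a rate monthly and provides DSMB review. A reader might infer that the plan leaves the most serious events unreported. The documents do not support that: a known hospital admission, for example, would go through section 12.0. What is affected is the analysed incidence and how systematically events come to light.

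A reader might also infer that someone who misses surveys cannot have an AE. That goes too far. The BDI-II is weekly and compared with baseline, so a rise that persists is caught at the next completed survey, and an event flagged before a participant stops answering still counts.

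Nor can the planned attrition be turned directly into a corrected rate. The plan says "To account for 20% attrition, we will enroll a maximum of 108 participants", but someone lost late may have several earlier BDI-II scores. The 20% is therefore not the share without post-baseline data, and enrolment above the target is meant to absorb some of it.

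There are partial routes by which events might surface: additional treatment tracked as an outcome (section 3.0), depression treatment from self-report and the EHR (section 4.0), calls after deterioration (section 13.0), and contact from physicians (section 12.0). None is a general AE enquiry, and none feeds the section 11.0 definition. The missing-data paragraph includes all randomised participants, allows imputation when more than 10% is missing, and checks differential dropout, but it is not tied to AEs.

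Finally, a targeted BDI-II safety outcome is defensible in a four-week app pilot. That stands, provided it is named as such and is not the whole definition of an AE.

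**Conclusion.** The concern holds as a conflict between section 11.0 and section 12.0, together with the lack of any stated general method for finding AEs. If section 11.0 is followed as written, the AE incidence excludes events that section 12.0 itself treats as AEs. It also misses transient events at skipped surveys and events after a participant stops responding.

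The size cannot be taken from the documents. Under the assumptions above, a fall from full to 80% capture lowers the chance of crossing the 5% test limit by 0.17 at a true rate of 10% (0.365 − 0.195) and by 0.22 at 15% (0.764 − 0.544). These figures show sensitivity to capture and do not predict this trial's result. The conclusion about the definitions does not depend on them.

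**What to change.** - In section 11.0, define an AE as any untoward event during follow-up learned from any source (weekly survey, risk call, participant, guardian or physician), with seriousness judged by the FDA criteria that section 12.0 already cites.
- Report BDI-II deterioration and BDI-II suicidality as two separately named safety outcomes.
- Add one open question to the existing weekly REDCap survey, in both arms, on new health problems, emergency visits or hospital stays.
- For the BDI-II outcomes, report by arm the number with no post-baseline BDI-II and the number of weekly surveys completed. Incidence can then be read against non-response. This discloses bias from worsening-related dropout but does not remove it.
- State which count the 5% test uses once the definition is widened. Sections 11.0, 12.0 and 13.0 attach 5% to three different numerators (all AEs, significant AEs, and serious or severe AEs related to deterioration), and these need to be reconciled.

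The cost is protocol wording and one survey item. The downside is more minor events to log and code each week.
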